6.2.1.5 Dosage Adjustments, Delays, Rules for Withholding or Restarting, Permanent Discontinuation

Dosage Adjustments

The subject should continue on the same dose of AMG 224 throughout the study unless the following events occur:

- For subjects experiencing an adverse event meeting the DLT definition or intolerable related adverse events BUT showing evidence of response, there will be an option to reduce the dose to the immediate next lower dose level (ie Dose Level -1 as outlined in [Table 3](#) or a further lower dose level (ie Dose Level -2 as outlined in [Table 3](#)).
- The study drug can be resumed once the adverse events recover to baseline or Grade 1 and the reintroduction of AMG 224 is deemed safe by the Investigator, Amgen's Medical Monitor, and Global Safety Officer.
- Subjects must be informed of the risk of continuing on therapy. Each subject is only allowed a single dose reduction.
- For subjects experiencing thrombocytopenia after the DLT-window, there will be an option to reduce the dose to the immediate next lower dose level (ie, Dose Level -1 as outlined in [Table 3](#)) or a further lower dose level (ie Dose Level -2 as outlined in [Table 3](#) in the dose expansion part of the study (as described in [section 6.3.1](#)).

The investigator should notify Amgen immediately before administration of the lower dose of AMG 224.

Subject who have been dose-reduced will have an option to receive the higher dose (ie, Dose Level -1 or Dose Level 1) at the next planned cycle if the adverse event resolves to \leq grade 1 or baseline and the reintroduction of AMG 224 at the higher dose is deemed safe by the Investigator.

For dose reduction level, refer to [Table 3](#):

Table 3. Dose Reduction of AMG 224 for Toxicity (Only in Dose Expansion)

Dose level	Dose IV Q3W
Dose Level 1	
Dose Level -1	
Dose Level -2	

Subjects should not be rechallenged with AMG 224 if the following AMG 224-related adverse events occur:

- Any life-threatening adverse events
- DILI (Drug Induced Liver Injury) meeting Hy's law

- Persistent grade 3 adverse events that do not recover to baseline or Grade 1 within 4 weeks. Any treatment-related adverse event meeting DLT-criteria that recurs

Dosage Delays

During the DLT-window, if the dosing is delayed for more than 7 days the subject will be removed from the study and will be replaced. After DLT-window, if the dosing is delayed for ≤ 3 weeks, the subject should resume the treatment as soon as possible if deemed safe by the investigator. The investigator should inform the Amgen Clinical team as soon as the unexpected dosing interruption occurs. If the dosing of AMG 224 is delayed more than 3 weeks (missing 1 cycle) due to treatment-related adverse events, the subject will be removed from the study. If the dosing delay occurred under conditions other than those associated with AMG 224 related toxicities, the case will be reviewed by Amgen medical monitor to determine whether the subject will be allowed to resume AMG 224 treatment.

Rules for Withholding or Restarting

AMG 224 should be withheld for any of the following:

- Suspected DLT (including AE that meet DLT definition outside DLT window)
- Grade 3 thrombocytopenia (follow the thrombocytopenia management in [Section 6.3.1](#))
- Aspartate aminotransferase (AST) or alanine aminotransferase (ALT) greater than 3x ULN or total bilirubin greater than 1.5x ULN

AMG 224 dosing can be resumed if the toxicities resolve to grade ≤ 1 or return to subjects' baseline values. The restarting of therapy should be deemed safe by the investigators and Amgen's medical monitor.

Rules for Permanent Discontinuation

Subjects will permanently discontinue from the investigational product if:

- Subjects experience adverse events meeting the DLT criteria at any time. Subjects will be followed until the DLT is resolved, returns to baseline value or is considered stable. Subjects will be withdrawn from AMG 224 treatment and will be treated as deemed appropriate by the investigator or treating physician. Except for:
 - Subjects showing evidence of response or subjects who in the opinion of the investigator may be responding to AMG 224, may have the option to continue therapy once the adverse events recover to baseline or Grade 1 and the re-introduction of AMG 224 is deemed safe by the investigator, Amgen's medical monitor, and Global Safety Officer. The subject should

restart at a reduced dose (see [Section 6.2.1.4](#)) subsection Dose Adjustments).

- Intolerability of the study treatment
- The dosing is delayed > 3 weeks due to AMG 224-related adverse events
- Disease progression according to IMWG response criteria
- Clinical significant deterioration of health status
- Withdrawal of informed consent
- Subjects become pregnant or is breastfeeding

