8. WITHDRAWAL FROM TREATMENT, PROCEDURES, AND STUDY

8.1 Subjects' Decision to Withdraw

Subjects have the right to withdraw from the study at any time and for any reason without prejudice to their future medical care by the physician or at the institution.

Subjects (or a legally acceptable representative) can decline to continue receiving investigational product and/or other protocol required therapies or procedures at any

time during the study but continue participation in the study. If this occurs, the investigator is to discuss with the subject the appropriate processes for discontinuation from investigational product or other protocol required therapies and must discuss with the subject the options for continuation of the Schedule of Assessments ([Table 5.](#)) and collection of data, including endpoints and adverse events. The Investigator must document the change to the Schedule of Assessments ([Table 5.](#)) and the level of follow-up that is agreed to by the subject (eg, in person, by telephone/mail, through family/friends, in correspondence/communication with other physicians, from review of the medical records).

Withdrawal of consent for a study means that the subject does not wish to receive further protocol-required therapies or procedures, and the subject does not wish to or is unable to continue further study participation. Subject data up to withdrawal of consent will be included in the analysis of the study, and where permitted, publicly available data can be included after withdrawal of consent. The investigator is to discuss with the subject appropriate procedures for withdrawal from the study.

8.2 Investigator or Sponsor Decision to Withdraw or Terminate Subjects' Participation Prior to Study Completion

The investigator and/or Amgen can decide to withdraw subjects from investigational product and/or other protocol required therapies, protocol procedures, or the study as a whole at any time prior to study completion.

Subjects may be eligible for continued treatment with Amgen investigational product(s) and/or other protocol required therapies by a separate protocol or as provided for by the local country's regulatory mechanism, based on parameters consistent with [Section 12.1.](#)

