8.3 Reasons for Removal From Treatment or Study

8.3.1 Reasons for Removal From Treatment

Reasons for removal from the investigational product include any of the following:

- subject request
- safety concern (eg, due to an adverse event)
- ineligibility determined
- protocol deviation
- non-compliance (eg, procedural or dosing as defined in [Section 6.2.1.1](#))
- requirement for alternative therapy
- pregnancy

- decision by Amgen (other than subject request, safety concern, or lost to follow-up)
- decision by investigator (other than subject request, safety concern, or lost to follow-up)
- death
- lost to follow-up
- Confirmed Disease Progression per IMWG ([Appendix D](#))

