8.3.2 Reasons for Removal From Study

Reasons for removal of a subject from the study are:

- decision by Amgen
- withdrawal of consent from study
- death
- lost to follow-up

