4.2 Subgroups

Biomarker data may be incorporated in additional exploratory subgroup or multivariate analyses. The analyses of biomarkers may be performed after collection of all samples

during the conduct of the study and therefore may be reported after the primary analysis of efficacy endpoints.

5. Definitions

Age at Enrollment

Subject age at enrollment will be determined using the age in years reported in the clinical database.

AUC_{0-3 week} = AUC_{0-504 hrs}

It is defined as the area under the concentration-time curve from time 0 to 504 hours.

Baseline

Unless otherwise specified the baseline value for parameters/assessments scheduled to be performed on the same day as the first administration of AMG 224 (Q3W), is the last value measured before the first administration of AMG 224 on that day. For parameters/assessments not scheduled to be performed (or scheduled but not performed) on the same day as the first administration of AMG 224, the baseline value is the value from the screening period measured closest to the day of first administration of AMG 224. In the event that multiple assessments are done on the same day as the first administration of AMG 224 and there is no time associated with the assessments, the value associated with the last clinically planned event before the first administration of AMG 224 will be used as the baseline value.

For baseline ECG, three triplicate ECGs to be collected ≥ 30 minutes apart, with each ECG in triplicate approximately 30 seconds apart (3 set collected predose on day 1 with total of 9 ECGs) planned to be taken predose. Mean value will be calculated and used in the analysis. The mean of the values within a triplicate should be calculated before taking the mean of the triplicate averages. Where an ECG is missing within a triplicate, all available data will be averaged for that time point.

Best Overall Response

Best overall response for a subject is the best observed post baseline disease response per the International Myeloma Working Group Uniform Response Criteria for Multiple Myeloma (IMWG-URC).

Best Overall Response/Progression CRF will be employed to determine the response.

Every effort should be made to document the objective progression even after discontinuation of treatment.

Body Mass Index (BMI)

Body Mass Index should be calculated using the following formula

$$\text{BMI (kg/m}^2\text{)} = \text{weight (kg)} / [\text{height (cm)} / 100]^2$$

Change From Baseline

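### The dosing-delay rule removes subjects from the study where the rest of the plan removes them from treatment; the two must be reconciled so that EOT, EOS and adverse-event follow-up are not dropped

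*Protocol*

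**What the plan says.** Protocol Section 6.2.1.5, under Dosage Delays, contains two rules that take a subject off the study:

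- Within the DLT window, for a delay of any cause: "if the dosing is delayed for more than 7 days the subject will be removed from the study and will be replaced".
- After the window, if dosing is "delayed more than 3 weeks (missing 1 cycle) due to treatment-related adverse events, the subject will be removed from the study".

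Further down the same section, the permanent-discontinuation list opens with "Subjects will permanently discontinue from the investigational product if" and includes "The dosing is delayed > 3 weeks due to AMG 224-related adverse events". The trigger is the same as in the second rule, but here the consequence is stopping the product.

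Section 8.3 keeps two separate lists. Section 8.3.1 puts adverse events under removal from treatment. Section 8.3.2, which begins "Reasons for removal of a subject from the study are", has four entries: sponsor decision, withdrawal of consent, death and loss to follow-up. Section 8.1 says that subjects who decline product may do so at any "time during the study but continue participation in the study". SAP Section 5, under Best Overall Response, adds: "Every effort should be made to document the objective progression even after discontinuation of treatment".

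**The concern.** The protocol treats leaving treatment and leaving the study as different things, with different follow-up. For one and the same event, a related toxicity that holds up dosing for more than 3 weeks, it gives both outcomes. A site that follows the Dosage Delays sentence literally could close the subject out at once. A site that follows the permanent-discontinuation list would perform the EOT and EOS visits, follow open adverse events and try to document progression.

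At stake are the EOT and EOS safety and disease assessments and any later progression information for the subjects concerned. In the 3-week case removal is defined by toxicity. If it also ends disease assessment, the censoring of time to progression and duration of response (SAP Section 5: at the last evaluable assessment) occurs for a reason that may be related to the drug's effect.

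**Working it through.** The plan gives no figure on this point. It states no rate of dosing delay, and its sample-size statements do not depend on one. The check is therefore a comparison of texts plus a day count.

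**Dispositions side by side**

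| Place | Trigger | Consequence |
|---|---|---|
| 6.2.1.5 Dosage Delays | > 7 days in DLT window, any cause | off study, replaced |
| 6.2.1.5 Dosage Delays | > 3 weeks, related adverse event | off study |
| 6.2.1.5 Permanent Discontinuation | > 3 weeks, related adverse event | off product |
| 6.3.1 | thrombocytopenia not manageable by standard care | off product |
| 8.3.1 | adverse event | off treatment |
| 8.3.2 | delay not listed | none |

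**Follow-up expected elsewhere once treatment stops**

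- 6.2.1.5: DLTs are followed to resolution, baseline or stability.
- 9.2.1.1: reported adverse events are followed until stable or reversed.
- Table 5, footnote 21: EOT and EOS examinations are to be attempted after any premature discontinuation.
- SAP Section 5: progression is to be documented after treatment ends.

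Table 5 places safety laboratory tests, ECG, neuropathy assessment, SPEP/UPEP and free light chains at both EOT and EOS.

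**Day count**

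Inputs: dose 1 on Day 1; dosing every 3 weeks, so dose 2 is due on Day 22; DLT window Days 1 to 28 (Section 3.1); EOS 30 to 37 days after the last dose (Sections 3.5.2 and 7.2.24).

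1. *The 7-day rule.* A delay of exactly 7 days reaches 22 + 7 = Day 29, so the rule triggers from Day 30, which is 29 days after dose 1. With the last dose on Day 1, EOS falls between 1 + 30 = Day 31 and 1 + 37 = Day 38. Removal on Day 30 therefore comes 1 to 8 days before the EOS visit. The ordinary DLT window has already closed.
2. *The 3-week rule.* The next dose is due 21 days after the last one, so the rule triggers more than 21 + 21 = 42 days after the last dose. The EOS window closed at day 37, at least 42 − 37 = 5 days before. What literal removal could still cost is the EOT visit, a late EOS visit, follow-up of the unresolved toxicity and later progression documentation.

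**What differs in the data**

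If only treatment stops, up to two further scheduled disease assessments (EOT and EOS) could enter time to progression and duration of response. If the subject leaves the study at once, neither is made. After EOS nothing is scheduled under either reading; only the SAP's request to document progression remains.

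**Replacement**

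Section 3.4 ties replacement to DLT-evaluability during dose exploration. The Dosage Delays sentence ties it to removal from the study. These are different concepts, and only the first is needed for the 3+3 count.

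**The case against.** The strongest reply is that little turns on the word. Section 3.5.2 ends the study for every subject off treatment at the EOS visit, and no efficacy visit is scheduled afterwards. Dosed subjects stay in the Safety Analysis Set whatever happens. Adverse-event, DLT and EOT/EOS follow-up is required elsewhere, so a careful site would do it anyway. Section 8.3.2 allows a sponsor decision, and Section 8.2 allows withdrawal from the study as a whole at any time. The 7-day sentence is not specific to toxicity. Time to progression and duration of response are descriptive secondary endpoints in a single-arm phase 1 study.

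Most of this stands, and it limits the size of the point. It does not remove the contradiction. An automatic removal rule is not clearly a sponsor decision, and the general follow-up duties are the ones that literal removal from the study would undercut.

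Two stronger readings are tempting, and the documents do not support either:

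- A reader might infer that the subjects with most toxicity lose their later safety and progression data, and put a number on it: assuming that 10 to 20% of 60 subjects are delayed gives 6 to 12 informatively censored. The delay rate has no source, the loss depends on how a site reads the text, and some of those subjects may already have progressed. Anyone stopping for toxicity without progression would be censored at about the same time, because follow-up ends at EOS.
- A reader might infer that a subject whose second dose is withheld for a DLT would be replaced and vanish from the DLT count. Section 6.2.1.2 limits replacement to reasons other than a DLT, so the text as a whole does not establish this. The point here does not rest on it.

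**Conclusion.** The concern holds as an internal contradiction with a limited, conditional consequence. Section 6.2.1.5 gives two dispositions for the same 3-week toxicity trigger, and its off-study wording does not fit Section 8.3, the follow-up duties or SAP Section 5.

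Read literally, it may drop the EOT and EOS safety and disease assessments and any later progression documentation for some subjects. Under the 7-day rule, removal falls 1 to 8 days before the EOS visit. Under the 3-week rule, the EOS window has already passed, and the reason for removal is toxicity by definition. The day count assumes dosing on schedule up to the delayed dose. How many subjects are affected cannot be derived from the documents, and no figure in the plan changes.

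**What to change.** Reconcile the Dosage Delays text with the permanent-discontinuation list in the same section, with Sections 8.3.1 and 8.3.2, and with SAP Section 5, so that study and treatment are used consistently. In doing so:

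- State that, whatever the treatment disposition, the EOT, EOS and adverse-event follow-up already in the protocol still applies, as does the SAP's progression documentation where it can be obtained.
- State that replacement concerns only the DLT-evaluable count.

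Which delay leads to which treatment decision is for the sponsor and investigators to settle; no threshold or stopping rule is suggested here.

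The cost is a wording change to the protocol and an aligned sentence in the SAP. The EOT and EOS visits are already scheduled. Progression documentation after EOS has no scheduled visit, so it should be asked for only where available.

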6.2.1.6 Dosage Limiting Toxicities

The grading of adverse events will be based on the guidelines provided in the Common Terminology Criteria for Adverse Events (CTCAE) version 4.0 (available online at <http://evs.nci.nih.gov/ftp1/CTCAE/About.html>). Determination of the severity of adverse events will be consistent with Common Terminology Criteria for Adverse Events (CTCAE) version 4.0. The relationship of an adverse event to investigational product will be determined by the Investigator. An event should be considered related to treatment if, in the Investigator's medical judgment, there is a reasonable possibility that the event may have been caused by AMG 224.

A DLT is defined as a Grade 3 or higher non-hematological or a Grade 4 hematologic adverse event that occurs during the DLT window (day 1 through day 28 after the administration of the first dose of AMG 224) in Part 1 Dose Exploration unless clearly attributable to causes other than AMG 224 treatment. DLT toxicities do not include fatigue, nausea, diarrhea, vomiting, neutropenia, anemia, thrombocytopenia and lymphopenia, increased serum creatinine or electrolytes abnormalities that are not clinically significant and require no treatment unless the following criteria are met:

Hematological toxicity:

- Grade 4 neutropenia lasting > 7 days
- Grade 3 or 4 neutropenia with fever > 38.5°C
- Grade 3 thrombocytopenia with ≥ Grade 2 hemorrhage
- Grade 4 thrombocytopenia lasting > 7 days
- Grade 3 anemia with symptoms or required intervention (eg, transfusion)
- Grade 4 anemia
- Lymphopenia of any grade is not considered a DLT

Approved

Non-hematological toxicity:

- \geq Grade 3 nausea, vomiting or diarrhea persisting more than 3 days despite optimal medical support
- Grade 3 fatigue persisting > 7 days
- \geq Grade 3 acute kidney injury (creatinine >3 X baseline or > 4.0 mg/dL) lasting > 3 days
- Elevation of either AST or ALT according to the following criteria:
 - $> 8x$ ULN;
 - $> 5x$ ULN but $< 8x$ ULN for ≥ 2 weeks;
 - $> 5x$ ULN but $< 8x$ ULN and unable to adhere to enhanced monitoring schedule; or
 - $> 3x$ ULN with clinical signs or symptoms that is consistent with hepatitis (such as right upper quadrant pain/tenderness, fever, nausea, vomiting, jaundice, rash or eosinophilia ($> 5\%$)).
- TBIL $> 3x$ ULN

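### Protocol 6.2.1.5 lets dosing resume after a post-window event that meets the DLT definition, while its next list stops treatment for that event unless the subject may be responding; no text ranks the two

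*Protocol*

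**What the plan says.** Four parts of Protocol 6.2.1.5 bear on what happens after an event of DLT severity.

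- **Rules for Withholding or Restarting.** Drug is held for "Suspected DLT (including AE that meet DLT definition outside DLT window". The restart sentence begins "AMG 224 dosing can be resumed if the toxicities resolve to grade": the threshold is grade 1 or the subject's baseline, and the investigators and the sponsor's medical monitor must consider it safe. Response is not a condition and no lower dose is required.
- **Rules for Permanent Discontinuation.** Subjects must stop for good when "Subjects experience adverse events meeting the DLT criteria at any time". The exception covers "Subjects showing evidence of response or subjects who in the opinion of the investigator may be responding to AMG 224". They may continue after recovery, should restart at a reduced dose, and need the Global Safety Officer's agreement as well as that of the investigator and medical monitor.
- **Dosage Delays.** After the DLT window, for a delay of up to 3 weeks, "the subject should resume the treatment as soon as possible if deemed safe by the investigator". DLT-criteria events are not carved out.
- **Dosage Adjustments.** A dose-reduction option exists "For subjects experiencing an adverse event meeting the DLT definition or intolerable related adverse events BUT showing evidence of response". A separate list, opening "Subjects should not be rechallenged with AMG 224 if the following AMG 224-related adverse events occur", bars restart after life-threatening events, Hy's law cases, Grade 3 events not recovered within 4 weeks, and recurrent DLT-criteria events.

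Section 6.2.1.6 supplies the severity threshold: "A DLT is defined as a Grade 3 or higher non-hematological or a Grade 4 hematologic adverse event", with listed carve-outs.

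**The concern.** The withholding list does not merely hold drug while a possible DLT is investigated. Its parenthesis takes in post-window events that do meet the definition, and its restart sentence turns on recovery, not on ruling the DLT out. The next list removes the same subject from treatment unless there is some sign of response. A site that resumes under the first list therefore breaches the second.

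At stake is whether a subject who is not benefiting is re-exposed, possibly at full dose, to a first-in-human antibody-drug conjugate after a dose-limiting type of toxicity. The medical monitor's agreement is a real check, but the monitor works from the same unranked text. Sites that read it differently would also produce discontinuation and exposure data that are not comparable.

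**Working it through.** No design figure is involved, so the check sets the rules side by side for one event: an adverse event after day 28 that meets the DLT definition and recovers to grade 1 or baseline.

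| Rule | Not judged possibly responding | Responder or possible responder | Named approvers |
|---|---|---|---|
| Withholding list | may resume, dose not stated | may resume, dose not stated | 2: investigator, medical monitor |
| Discontinuation list | stop permanently | may resume, should be at a reduced dose | 3: those two plus Global Safety Officer |
| Dosage Delays (up to 3 weeks) | should resume | should resume | 1: investigator |

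The second column is a contradiction between permission and prohibition. In the third column the rules differ only on dose and sign-off.

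**Does another section rank them?**

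- *6.2.1.2* lets the DLRT classify certain post-window events as DLTs by unanimous decision. It does not say which restart rule then applies.
- *Dosage Adjustments* leans toward the discontinuation rule by tying the option to response. It differs from the exception in three ways: it omits possible responders; it gives responders with intolerable related events an option, whereas the discontinuation list makes intolerability a stop without exception; and it makes the reduction optional.
- *6.3.4* holds drug temporarily for Grade 3 or 4 neuropathy, and *6.3.5* allows resumption after Grade 3 or 4 arrhythmia. Neither mentions response or the discontinuation rule.
- *9.1.1* leaves removal for an adverse event to the investigator's judgment.
- *Table 4* (platelets) and *6.4* (hepatic events) carry their own rules.
- The exception's pointer for dose reduction, and 6.4.3's pointer for permanent discontinuation, both go to 6.2.1.4, which holds the enrollment stopping rules.
- The SAP contains no restart rule.

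**Worked case.** Take an illustrative first, related Grade 3 fatigue lasting 10 days in cycle 5, in a subject without progression whom the investigator does not think is responding. Section 6.2.1.6 counts Grade 3 fatigue beyond 7 days, and no part of 6.3 deals with fatigue.

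- Dose days are 1 + 21k, so cycle 5 is day 1 + 21 × 4 = 85 and cycle 6 is due on day 1 + 21 × 5 = 106.
- Onset between day 85 and day 106 (before dosing) gives recovery between day 95 and day 116. The cycle 6 delay is max(0, recovery day − 106) = 0 to 10 days, below the 21-day limit.
- Recovery in 10 days is within the 4 weeks (28 days) allowed for Grade 3 events, so the no-rechallenge list does not apply.
- The withholding list permits cycle 6. If the dose is late, Dosage Delays also favours it. The discontinuation list ends treatment.

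Grade 3 neuropathy of the same length gives the same split, with 6.3.4 as a further text on the side of resuming.

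**The case against.** The strongest reply is that the rules can be obeyed together. Permission to resume yields to an order to stop; a site that withholds and then discontinues breaches neither list; and Dosage Adjustments points the same way. The generic restart sentence would still serve Grade 3 thrombocytopenia and liver-test elevations. Together with the DLRT route in 6.2.1.2, this supports a sensible sequence of hold, assess, then discontinue if confirmed. As a reading of intent this largely stands. It does not close the gap, because the sequence is not written down, the parenthesis already includes events that meet the definition, and Dosage Delays, 6.3.4 and 6.3.5 give a site reasonable grounds to resume.

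It could also be said that DLTs exist only in the first 28 days of Part 1, as 6.2.1.6 frames them. Both lists expressly reach beyond the window, so that does not help.

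The safeguards are real: recovery and two approvers under the withholding list, the no-rechallenge bars, and a broad discretionary exception for possible responders. They limit the harm without deciding which list applies. The wrong cross-references alone are editorial, since the intended targets can be worked out.

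Two stronger readings are tempting and not supported. A reader might infer that MTD estimation is compromised. Protocol 10.4.2.3 limits the primary DLT analysis to events inside the evaluation interval and places later ones in a sensitivity analysis, which SAP 9.6.1.2 makes optional. A reader might also infer that the conflict is common because most dosing is post-window. Only days 1 and 22 fall in the window, so 4 of the 6 doses assumed in Table 6 (67%) come later. That is a share of planned doses if nobody stops early; it says nothing about how often a qualifying event occurs.

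**Conclusion.** The inconsistency is real and should be fixed, within limits. Stop versus resume is in doubt only for a first, related, recovering, non-life-threatening DLT-criteria event that is not already settled by Table 4, Section 6.4, the no-rechallenge list or the 3-week delay limit, in a subject not judged possibly responding. For responders and possible responders, what is unsettled is whether the restart should be at a reduced dose and whether the Global Safety Officer must agree. The discontinuation rule is the likelier intent, but that is inference from its mandatory wording and from Dosage Adjustments. The documents give no rate for such events, so no frequency is claimed.

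**What to change.** Add a precedence paragraph to 6.2.1.5 to this effect:

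- AMG 224 is withheld while a suspected DLT-criteria event, inside or after the window, is assessed by the investigator and medical monitor, or by the DLRT where 6.2.1.2 applies.
- If the event does not meet the criteria, or clearly has another cause, dosing may resume under the withholding rule.
- If it meets the criteria, the discontinuation rule and its exception for responders and possible responders govern. The restart provisions under Withholding, Dosage Delays, 6.3.4 and 6.3.5 then do not apply.
- Thrombocytopenia after cycle 2 in dose expansion follows Table 4. DLT-criteria thrombocytopenia in cycles 1 and 2, or in Part 1, stays under the discontinuation rule, because Table 4 starts after the second cycle and uses the expansion-only dose levels of Table 3.
- Hepatic events follow Section 6.4.

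Align Dosage Adjustments with the exception on three points: possible responders, whether responders with intolerable related events may continue at a lower dose, and whether the reduction is optional. Correct the two references to 6.2.1.4: to 6.2.1.5 in the exception, and to 6.2.1.5 or 6.4.1, as intended, in 6.4.3.

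The cost is a clarifying amendment, with no extra patients, visits or procedures.
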